### 5.7.2 Compensation

There is no compensation for participation in this study. Travel/accommodations for the participant may be provided for out-of-town participants or for those for whom traveling to NIH is a hardship. In such

cases, travel/lodging for the participant and one traveling caregiver may also be provided. If unexpected travel related expenses occur, participants may be provided with a voucher.

Employees and staff who participate during work hours must have permission from their supervisor and cannot receive compensation. NIH employees must either participate outside of work hours or take leave in order to receive compensation. NIH employees must take leave in order to accompany family members to appointments for research participation during their duty hours.

# **6** STUDY INTERVENTION

# 6.1 STUDY INTERVENTIONS(S) ADMINISTRATION

### 6.1.1 Study Intervention Description

This study intervention includes an investigational medical product (IMP), a non-investigational medicinal product (NIMP), and potentially an investigational MRI scanner.

### 6.1.1.1 Investigational medicinal product

The IMP is tolebrutinib, provided in the form of 60-mg tablets.

# 6.1.1.2 Non-investigational medicinal product

Approved anti-CD20 antibody therapy for participants not in the tolebrutinib cohort. Participants who wish to do so may, in consultation with their primary non-NIH clinician, switch to a different anti-CD20 therapy after week 48.

### 6.1.1.3 *Devices*

The primary 7-tesla MRI scanner and relevant accessories, as well as the pulse sequences used in this study, are FDA-approved, and their use conforms to the corresponding FDA labels.

If for any reason the primary 7-tesla MRI scanner is not available, another 7-tesla or (less preferred) 3tesla scanner may be used under conditions designated by the FDA as constituting nonsignificant risk under 21 CFR 812.2(b)(1). Acquisition parameters may be modified within the permitted range. These studies may also involve image reconstruction and analysis software, including research pulse sequences. In addition, the following non-FDA-approved systems may be used in this study under conditions designated by the FDA as constituting nonsignificant risk, with assurances from the manufacturer that all measures found in FDA-approved MRI are operational.

Justification for MRI, image reconstruction and analysis software, and head coil non-significant risk (NSR) designation

- Magnetic resonance imaging system (7T and 3T MRI) operating in research mode and with research pulse sequences
- MAGNETOM 7T scanner (manufactured by Siemens)
- Image reconstruction and analysis software
- 1Tx 32Rx Head Coil (manufactured by Nova Medical; tested and supplied by Siemens)

According to 21 CFR 812.3 (m) and FDA "Information Sheet Guidance for IRBs, Clinical Investigators, and Sponsors: Significant Risk and Nonsignificant Risk and Nonsignificant Risk Medical Device Studies January 2006," the use of these devices in the study are a Non-significant Risk study. 21 CFR 812.3(m) enumerates four criteria for a Significant Risk Device Study; none of these apply to this study:

- is intended as an implant and presents a potential for serious risk to the health, safety, or welfare of a subject.
  - None of the devices are implants.
- is purported or represented to be for a use in supporting or sustaining human life and presents a potential for serious risk to the health, safety, or welfare of a subject.

37

None of the devices are for use in supporting or sustaining human life.

• is for a use of substantial importance in diagnosing, curing, mitigating, or treating disease, or otherwise preventing impairment of human health and presents a potential for serious risk to the health, safety, or welfare of a subject.

The investigational use of the devices is not of substantial importance in diagnosing, curing, mitigating, or treating disease, or otherwise preventing impairment of human health.

• otherwise presents a potential for serious risk to the health, safety or welfare of a subject.

The protocol will comply with the abbreviated IDE requirements under 21 CFR 812.2(b).

# 6.1.2 Dosing and Administration

# 6.1.2.1 Dose Escalation

As of January 20, 2023, participants (n=4) who started tolebrutinib 60 mg/day and previously escalated to 120 mg/day† at Week 48 will remain at that dose. Participants (n=3) who initiated tolebrutinib 60 mg/day and did not escalate to 120 mg/day due to the partial clinical hold will be followed on study for an additional 48 weeks, according to the schedule of the Initial Cohort. They will furthermore be eligible to continue taking tolebrutinib 60 mg/day until tolebrutinib becomes FDA-approved or the clinical development program is terminated.

6.1.2.2 Dose Limiting Toxicity

Dose-limiting toxicity has not been established.

### 6.1.2.3 Dose Modifications

Should tolebrutinib 120 mg/day prove intolerable, the dose may temporarily or permanently be reduced to 60 mg/day. Participants will contribute to subsequent data analyses even if the dose is reduced. Treatment might need to be interrupted or permanently discontinued if deemed necessary due to an adverse event (Sections 7 and 8.4).

### 6.1.2.4 Drug Administration

As of January 20, 2023, participants (n=3) who have received one 60-mg tablet of tolebrutinib per day will no longer have the option to increase to 120 mg (2 tablets) per day at Week  $48^1$ . The tablet(s) should be taken orally with food. The time of day should be as consistent as possible throughout the study. Missed doses will not be made up.

Study interventions will be dispensed at regular site visits. Tolebrutinib dosing will continue for the duration of the study and may be continued thereafter until tolebrutinib is either marketed or its development halted.

# 6.1.2.5 Partial Clinical Hold

On June 29, 2022, we were informed by Sanofi that as of June 27, 2022, new enrollment was being halted across all 5 of their US phase 3 trials of tolebrutinib, and that all participants dosed after April 29, 2022 in the US would be required to stop tolebrutinib but would continue for observation on the trials. Sanofi staff detailed a call earlier in the week, on which the FDA verbally communicated a partial clinical hold to the Sponsor. The partial clinical hold was enacted after internal discussions regarding four participants with evidence of drug-induced liver injury (DILI), and the FDA outlined specific steps that Sanofi could take to support lifting the hold.

On July 12, 2022, the FDA issued a partial clinical hold to the NINDS IND as well, with identical stipulations to the Sanofi hold. As such, until the hold is lifted, we will not initiate new subjects on tolebrutinib. However, as no participants in our study had been taking tolebrutinib for less than 60 days at the time of

<sup>† See Section 6.1.2.5

the FDA partial clinical hold, the FDA does not require that we stop tolebrutinib for any participant in our trial. Furthermore, although not specifically stipulated by the FDA, we have elected to defer dose escalation from 60 to 120 mg (the "week 48" time point) until the partial clinical hold is lifted or modified; once the dose is escalated, however, the trial clock will restart.

On January 20, 2023, the FDA requested a revision to the protocol to remove the potential for dose escalation. Participants who have initiated tolebrutinib 60 mg and escalated to 120 mg/day will remain at that dose. The 3 remaining participants who initiated tolebrutinib 60 mg will remain at 60 mg and not be escalated to 120 mg/day.

# 6.2 PREPARATION/HANDLING/STORAGE/ACCOUNTABILITY

# 6.2.1 Acquisition and Accountability

Sanofi-Genzyme will ship tolebrutinib 60-mg tablets directly to the NIH clinical Center Pharmacy.

# 6.2.2 Formulation, Appearance, Packaging, and Labeling

Tolebrutinib tablets will be packaged in blister packs protected by a wallet. Each wallet contains 20 tablets which are dispensed in sufficient amount to cover patient treatment until the next study visit. Each wallet will be labeled. The packaging may be updated during the course of the study.

# 6.2.3 Product Storage and Stability

Tolebrutinib kits must be stored between 36°F and 86°F. Procedures for temperature monitoring and excursion management will be followed as per Sanofi's pharmacy manual. Tolebrutinib kits will be stored in a secure location in accordance with local regulations, labeling specifications, policies and procedures.

# 6.2.4 Preparation

Tolebrutinib will be supplied as a 60-mg oral tablets and will not require any preparation.

# 6.3 MEASURES TO MINIMIZE BIAS: RANDOMIZATION AND BLINDING

Participants will not be randomized in this study. Up to 10 adults with MS who are on stable disease modifying treatment with anti-CD20 antibody therapy and are within 6 months of their most recent dose, have at least one paramagnetic rim lesion on 7-tesla magnetic resonance imaging (MRI), and have developed no new white matter lesions or clinical relapses for at least 6 months, will receive treatment with tolebrutinib 60 mg/day or escalating to 120 mg/day and agree to forego further anti-CD20 or other disease-modifying therapy for the duration of the trial.‡ A comparison cohort of individuals who meet enrollment criteria (other than tolebrutinib contraindications) but choose not to take tolebrutinib will continue to receive their current anti-CD20 therapy.

The study is unblinded for the participant and investigators, except for the investigators performing analysis of the raw MRI data for the primary and secondary outcomes, who will be blinded to the time point at which the data were acquired. If these investigators become unblinded, their analysis will be scrapped and redone by blinded investigators.

# 6.4 STUDY INTERVENTION COMPLIANCE

At the end of the baseline visit (Day 0), the participant will receive the study intervention for the following 144 weeks (Cohort A) before entering the extension phase. At each following visit, a new kit will be dispensed, and the participant will self-administer the medication. Participants will be asked to track daily dosage either electronically or in a written format per their preference. They will be provided with a template drug diary, which they may opt to use. Remaining pills will be counted at each follow-up visit to assess overall drug compliance.

# 6.5 CONCOMITANT THERAPY

<sup>‡ See Section 6.1.2.5

Concomitant therapies (including over-the-counter or prescription medicines, vitamins, and/or herbal supplements) will be reviewed at each study visit and documented in the clinical chart.

Use of certain medications will be restricted during study participation, as detailed in Section 5.2 and below.

The following medications will be prohibited throughout study participation in the tolebrutinib cohorts:

- Other MS disease-modifying treatments
- Acetylsalicylic acid (aspirin)
- Anti-platelet drugs (e.g., clopidogrel)
- Anticoagulants, including:
  - Warfarin
  - Heparin, including low-molecular-weight heparins
  - 0 Dabigatran
  - Apixaban, edoxaban, rivaroxaban
- Potent and moderate inducers and inhibitors of cytochrome P450 3A (CYP3A) or potent inhibitors of CYP2C8 hepatic enzymes as listed in Appendix 1.

In the tolebrutinib cohorts, short courses (up to 5 days) of NSAIDs (other than acetylsalicylic acid) at the recommended dose may be used if clinically indicated. Standard treatment of MS relapse with high dose glucocorticoids is permitted.

### 7 STUDY INTERVENTION DISCONTINUATION AND PARTICIPANT DISCONTINUA-TION/WITHDRAWAL

### 7.1 DISCONTINUATION OF STUDY INTERVENTION

Participants are free to withdraw from participation in the study at any time upon request.

The PI or MAI may discontinue or withdraw a participant from the study for any of the following reasons:

- Disease activity or progression that requires discontinuation of the study intervention
- If any clinical adverse event (AE), laboratory abnormality, or other medical condition or situation occurs such that continued participation in the study would not be in the best interest of the participant
- Investigator judgment for safety, behavioral, compliance, or administrative reasons
- Positive pregnancy test

The reason for withdrawal or discontinuation will be documented in the medical record. Participants will be asked to return for a follow-up visit within 3 months, and ideally within 1 month after discontinuation of the intervention.

Events of Special Interest (Section 8.4.7) will follow the algorithm outlined in Appendix 2.

### 7.1.1 Definitive discontinuation

Definitive discontinuation is any IMP discontinuation associated with the definitive decision of the PI not to re-expose the participant to the IMP at any time during the study, or from the participant not to be re-exposed to the IMP, whatever the reason.

Definitive discontinuation will ensue for any confirmed treatment-related serious adverse event.

If discontinuation is due to adverse event preventing further exposure to the IMP, the participant will be followed up to recovery or stabilization of the event.

If possible, and after the definitive discontinuation of intervention, participants will be assessed using the

procedure normally planned for Week 24 if prior to Week 24, or the next protocol timepoint if they drop out at any later time. Details are provided in the Schedule of Activities (Section 1.3).

### 7.1.2 Temporary discontinuation

Temporary IMP discontinuation will ensue during evaluation of any suspected IMP-related serious adverse event. For all temporary IMP discontinuations, the duration of the discontinuation should be recorded by the PI or designee in the appropriate pages of the study record. Temporary discontinuation of study drug will be discussed with the IMM. Temporary IMP discontinuation decided by the PI or MAI corresponds to >1 dose not administered to the participant.

The current NIH treatment guidelines recommend against the use of BTK inhibitors in the treatment of COVID-19 unless a patient is enrolled in a clinical trial studying that indication. The guidelines are being updated regularly. If a trial participant on tolebrutinib treatment is hospitalized for COVID-19, the PI and MAI will discuss the case with the treating physician and appropriate experts to determine whether IMP will be continued or halted based on patient safety. Participants who are off of tolebrutinib for more than 12 weeks will not contribute to the primary analysis, although they can resume IMP and trial participation when determined by the PI, MAI, and treating physician.

### 7.1.2.1 Rechallenge

Re-initiation of intervention with tolebrutinib may be considered under close and appropriate clinical/and or laboratory monitoring if the PI or MAI determine in conjunction with either the study HAC or DSMB (see Section 10.6 and Appendix 2), according to his/her best medical judgment, that the responsibility of tolebrutinib in the occurrence of the concerned event was unlikely and if the selection criteria for the study are still met.

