## 5.2.1 Tolebrutinib Cohorts Exclusion Criteria

- 1. Pregnancy or lactation
- 2. MS relapse in the 6 months prior to dosing
- 3. Febrile illness within 4 weeks prior to dosing, or persistent chronic or active infection requiring treatment with systemic antibiotics, antivirals, or antifungals.
- 4. Treatment with another investigational drug or other investigational intervention within 3 months prior to baseline.
- 5. Contraindications for 7-tesla MRI
- 6. Presence of screening laboratory or ECG values outside normal limits that are considered in the PI or MAI's judgment to be clinically significant, including but not limited to:
  - a. Presence of liver injury defined as underlying hepatobiliary disease or screening alanine aminotransferase (ALT) more than 1.5 times the upper limit of normal (ULN)
  - b. At screening, positive for hepatitis B surface antigen and/or hepatitis B core antibody and/or positive for hepatitis C antibody
  - c. Any of the following:
    - i. Bleeding disorder or known platelet dysfunction at any time prior to the first screening visit
    - ii. Platelet count less than 150,000/µL at the screening visit
  - d. Lymphocyte count less than 1000 cells/dL at the screening visit
- 7. Is HIV-positive
- 8. Has received any live (attenuated) vaccine (including but not limited to varicella zoster, oral polio, and nasal influenza) within 2 months before dosing
- 9. Has received any of the following medications/treatments within the specified time frame before baseline assessment:

Medication	Exclusionary if used/used within re- quired wash-out period
Systemic corticosteroids, adrenocorticotropic hor- mone (other than used for premedication)	1 month prior to baseline MRI scan
Dimethyl fumarate	6 months prior to dosing
Intravenous immunoglobulin, fingolimod,	6 months prior to dosing

natalizumab	55
Teriflunomide	2 years prior to dosing or 1 month prior
	to dosing if participant undergoes an
	accelerated elimination procedure and
	has documented teriflunomide plasma
	level below 0.02 mg/L before dosing
Mildly to moderately immunosuppressive/chemo-	6 months prior to dosing
therapeutic medications such azathioprine and	
methotrexate	
Highly immunosuppressive/chemotherapeutic	2 years prior to dosing
medications: mitoxantrone up to 120 mg/m2 body	
surface area, cyclophosphamide, cladribine	
Alemtuzumab	4 years prior to dosing
Lymphoid irradiation, bone marrow transplanta-	Any time
tion, mitoxantrone (with evidence of cardiotoxi-	

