city following treatment, or cumulative lifetime	
dose >120 mg/m2), other strongly immunosup-	
pressive treatments with very long-lasting effects	
Any BTK inhibitor	Any time

- 10. Is receiving potent and moderate inducers and inhibitors of cytochrome P450 3A (CYP3A) or potent inhibitors of CYP2C8 hepatic enzymes as listed in Appendix 1.
- 11. Is receiving anticoagulant/antiplatelet therapies, including:
  - a. Acetylsalicylic acid (aspirin); half-life elimination: Parent drug: Plasma concentration: 15 to 20 minutes; Salicylates (dose dependent): 3 hours at lower doses (300 to 600 mg), 5 to 6 hours (after 1 g), 10 hours with higher doses
  - b. Antiplatelet drugs (eg, clopidogrel); half-life: 6 hours
  - c. Warfarin (vitamin K antagonist); half-life: 20-60 hours
  - d. Heparin, including low molecular weight heparin (antithrombin agents); half-life: 60-90 minutes
  - e. Dabigatran (direct thrombin inhibitor); half-life:12-17 hours
  - f. Apixaban (IV half-life: approximately 5 hours, oral half-life: approximately 12 hours), edoxaban (half-life: 10-14 hours), rivaroxaban (half-life: 5-9 or 11-13 hours in younger or elderly individuals, respectively) (direct factor Xa inhibitors)

Note: All above drugs need to be stopped at least 5 half-lives before study drug administration except for aspirin, which needs to be stopped at least 8 days before.

- 12. Has a history or presence of significant other concomitant illness that, according to the PI or MAI's judgment, would adversely affect participation in this study; examples include but are not limited to clinically significant cardiovascular, renal, hepatic, or metabolic disease.
  - Acute liver disease, cirrhosis, chronic liver disease (unless considered stable for >6 months)
  - Has untreated hepatitis C
  - Has chronic hepatitis B unless stable on oral suppression and/or followed by a local hepatologist to monitor for reactivation
  - Has active alcohol use disorder
  - Has an alcohol intake greater than 2 drink per day for men, and greater than 1 drink per day for women (1 drink = approximately 14 grams of alcohol = 350 ml beer = 140 mL wine = 40 mL of spirits)
  - Has aspartate transaminase (AST) or alanine transaminase (ALT) levels greater than 1.5x

ULN

- Has a total bilirubin level greater than 1.5x ULN unless due to Gilbert's or non-liver related disorder
- Has an alkaline phosphatase level greater than 2x ULN unless caused by non-liver related disorder or explained by a stable chronic liver disorder

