### 12.2 APPENDIX 2: Adverse Events of Special Interest (AESI)

In ANY CASE REQUIRING HAC REPORTING, INFORM the PI, HAC and Sponsor and follow the instructions below:

- INVESTIGATE specifically for malaise with or without loss of consciousness, dizziness, and/or hypotension and/or episode of arrhythmia in the previous 72 hours; rule out muscular injury
- EVALUATE for alternative causes
- CONSULT with a hepatologist
- PERFORM the following tests:
  - LFTs: AST, ALT, alkaline phosphatase, total and conjugated bilirubin, GGT and prothrombin time/ INR
  - o CPK, serum creatinine, complete blood count
  - Anti-HAV lgM, anti-HBc lgM, HBsAg, (HBV-DNA if clinically indicated), anti-HCV and HCV RNA, and anti-HEV lgM antibodies
  - Auto-antibodies: antinuclear, ANCA, anti-dsDNA, anti-smooth muscle, anti-LKM, anti-mitochondrial
  - Hepatobiliary ultrasonography (or other imaging and/or biopsy investigations if needed)
- DEPENDING on the clinical context, check for recent infection with EBV, CMV, herpes viruses, and toxoplasma
- CONSIDER iron, ferritin, transferrin saturation
- CONSIDER, DNA test for Gilbert's disease if clinically indicated
- CONSIDER patient hospitalization if INR>2 (or PT<50%) and/or central nervous system disturbances suggesting hepatic encephalopathy
- MONITOR transaminases and total bilirubin levels as closely as possible every 48 hours to every week until transaminases and/or total bilirubin levels are down-trending, then monitor every 2

61

scheduled visit.

weeks until 2xULN for transaminases and 1xULN for total bilirubin and then monitor every

• SEND expedited (<15 days) reports to the FDA of any cases with transaminases >8x ULN or >3x ULN with total bilirubin >2x ULN.

RECHALLENGE: Re-initiation of the study drug can only be considered after discussion with the HAC, PI, DSMB and study Sponsor once the ALT/AST decrease below 2xULN and/or TBL decrease below 1xULN and there is no clinical contraindication. In case it is agreed to re-start the study drug, ALT, ALT, TBL and ALP will be assessed weekly for the 1st month and, then, monthly for the 2nd and the 3rd month. The occurrence of new elevations above 3xULN for the ALT/AST values will lead to permanent discontinuation of the study drug.

(**Optional**) FREEZE serum sample (5ml x 2)

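### Section 7.1.2.1 and Appendix 2 set different conditions for considering a tolebrutinib restart after a liver event, and Appendix 2's own wording is loose on recovery limits and omits AST from the post-restart panel

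*Combined protocol and SAP*

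**What the plan says.** Section 7.1.2.1 (Rechallenge) lets re-initiation be considered, under close monitoring, on a decision that the PI or MAI reaches "in conjunction with either the study HAC or DSMB". What they must find is "that the responsibility of tolebrutinib in the occurrence of the concerned event was unlikely and if the selection criteria for the study are still met". The section points to Appendix 2.

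The selection criteria it relies on are in Section 5.2.1. Item 12 lists, for transaminases as multiples of ULN, "Has aspartate transaminase (AST) or alanine transaminase (ALT) levels greater than 1.5x". For bilirubin the same item lists "Has a total bilirubin level greater than 1.5x ULN unless due to Gilbert's or non-liver related disorder".

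Appendix 2 (Section 12.2) has its own rechallenge paragraph. On who takes part it says: "Re-initiation of the study drug can only be considered after discussion with the HAC, PI, DSMB and study Sponsor". Its laboratory condition for that step is "once the ALT/AST decrease below 2xULN and/or TBL decrease below 1xULN". A clinical contraindication also rules a restart out. The testing required after a restart reads "ALT, ALT, TBL and ALP will be assessed weekly for the 1st month"; in months two and three it becomes monthly. New ALT/AST elevations above 3xULN lead to permanent discontinuation.

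Four other places bear on the point:
- Section 7.1 says Events of Special Interest follow the Appendix 2 algorithm.
- Section 8.4.7 says the same, adds a separate HAC charter, and lists ALT, AST and bilirubin rises as separate triggers.
- Section 7.1.1 requires definitive discontinuation after any confirmed treatment-related serious adverse event.
- Section 10.6.1 leaves the HAC's responsibilities and workflow to its charter.

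**The concern.** Section 7.1.2.1 names the HAC and cites Appendix 2, so it appears to cover liver events as well as others. Appendix 2 does not refer back. A reader with a liver case therefore finds two sets of conditions and no statement of whether one replaces the other or both apply.

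Inside Appendix 2, two further details matter. The connector between the two recovery limits is ambiguous, and the test list after restart does not match the stopping rule that depends on it.

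The stake is participant safety and consistent conduct. Section 2.3.1 lists drug-induced liver injury (DILI), including severe injury, as an identified risk. Section 6.1.2.5 records that liver injury led to the partial clinical hold. Section 2.3.3 relies on the DILI monitoring plan and the HAC when it concludes that benefits outweigh risks. Recruitment to the tolebrutinib cohort has ended, but the seven treated participants (four on 120 mg, three on 60 mg) may continue until the drug is marketed or its development stops, so the rule is still in use.

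**Working it through.** No sample size, power or error-rate figure is involved. The check sets the two rules side by side and runs them as logical conditions.

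**Step 1: the conditions.**

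| Item | Section 7.1.2.1 | Appendix 2 |
|---|---|---|
| Who takes part | PI or MAI, with either the HAC or the DSMB | HAC, PI, DSMB and sponsor |
| Causality | Drug's responsibility unlikely | No condition |
| ALT and AST | Not above 1.5xULN (via Section 5.2.1) | Below 2xULN |
| Total bilirubin | Not above 1.5xULN, with exceptions (via Section 5.2.1) | Below 1xULN |
| How the limits join | Both must hold | And/or |
| Other | Close monitoring | No clinical contraindication |

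Neither rule is uniformly stricter. Section 7.1.2.1 is tighter on transaminases (by 2.0 − 1.5 = 0.5xULN) and on causality. Appendix 2 is tighter on bilirubin (by 1.5 − 1.0 = 0.5xULN) and on who must take part.

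**Step 2: where they disagree.** Let T be the higher of ALT and AST, and B total bilirubin, both as multiples of ULN.
- Appendix 2, literal: T < 2 or B < 1.
- Appendix 2, joint: T < 2 and B < 1.
- Section 7.1.2.1: T ≤ 1.5 and B ≤ 1.5 and causality unlikely.

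The values below are assumed for illustration. They take the required consultations as done, no clinical contraindication, and no bilirubin exception.

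| T | B | Causality unlikely? | App. 2 literal | App. 2 joint | Section 7.1.2.1 |
|---|---|---|---|---|---|
| 6.0 | 0.8 | Yes | Met | Not met | Not met |
| 1.8 | 0.8 | Yes | Met | Met | Not met |
| 1.2 | 0.8 | No | Met | Met | Not met |
| 1.2 | 1.2 | Yes | Met | Not met | Met |
| 1.2 | 0.8 | Yes | Met | Met | Met |
| 6.0 | 2.5 | Yes | Not met | Not met | Not met |

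Rows 2 and 3 separate the two sections on either reading of Appendix 2. Row 4 separates them on the joint reading. Row 1 shows what the literal and/or does: normal bilirubin meets the laboratory condition while transaminases are still high.

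**Step 3: the connector within Appendix 2.** The monitoring bullet in the same appendix continues two-weekly testing down to the same two limits, 2xULN for transaminases and 1xULN for bilirubin, but joins them with *and*. The appendix therefore uses two connectors for one pair of limits.

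**Step 4: AST after restart.** The weekly and monthly panel names ALT twice, bilirubin and alkaline phosphatase. The stopping rule uses ALT and AST. AST is in the scheduled liver tests (Section 8.3). In Section 1.3, however, these fall mostly 12 weeks apart after Week 12 (Cohort A adds Weeks 52 and 56) and 24 weeks apart in the extension. The three-month panel runs about 13 weeks. In the extension it could fall wholly between two scheduled visits, with no AST test required by either list.

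**The case against.** The strongest reply is that Section 7.1.2.1 is a general rule for any event, Appendix 2 is the specific rule for liver events, and Sections 7.1 and 8.4.7 make Appendix 2 the one to follow. The HAC charter, which is not available here, may settle the rest. This reading is natural, but no text says that the general conditions then cease to apply, and Section 7.1.2.1 itself names the HAC. It also leaves the and/or and the missing AST untouched.

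Several stronger conclusions are tempting but not supported:

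- **The rules cannot both be followed.** A reader might infer this, but each states conditions for considering a restart, and neither orders one. A team could satisfy both together. What is missing is a statement that it must.
- **Appendix 2 authorises restart before transaminases recover.** It only permits restart to be considered, after discussion with the HAC, PI, DSMB and sponsor and with no clinical contraindication. Speaking of a value that decreases suggests an analyte that had been raised, so and/or may have meant whichever was elevated. That is a plausible intention, not what the sentence says.
- **AST is dropped from liver follow-up.** It remains in the work-up, in monitoring of the event and in the scheduled tests. Only the post-restart list lacks it, probably through a typing slip.
- **Any drug-related liver injury could be rechallenged.** Section 7.1.1 rules this out for confirmed treatment-related serious events. The gap is confined to events that are non-serious or not confirmed as related, which the 3xULN triggers can capture.

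The 1.5xULN limits in Section 5.2.1 also sit under items that invoke PI or MAI judgement. How binding they are at rechallenge is therefore itself unclear, which is a further reason to clarify.

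**Conclusion.** The point stands as an inconsistency in an operative safety rule and should be corrected. The two sections differ on bodies involved, causality and both laboratory limits. The zones of disagreement are transaminases above 1.5 and below 2xULN, bilirubin from 1 to 1.5xULN (if Appendix 2's limits are read jointly), and events for which the drug's responsibility is not judged unlikely and Section 7.1.1 does not already bar restart.

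Two defects remain whichever section governs: the and/or, and the absence of AST from the post-restart panel.

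This rests on the protocol text alone, on reading still-met selection criteria as including the Section 5.2.1 liver limits, and on the HAC charter not already resolving the matter. How often such a case would arise cannot be estimated from the documents. No sample-size or primary-analysis figure depends on it.

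**What to change.** Reconcile Section 7.1.2.1 with the rechallenge paragraph of Appendix 2, together with Sections 5.2.1, 7.1, 7.1.1 and 8.4.7. The amended text should state:

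- which passage governs liver events, or that both apply;
- which bodies must be involved, and whether they decide or are consulted;
- whether the causality condition applies to liver events;
- how the laboratory limits combine, with an unambiguous connector in place of and/or;
- a post-restart panel, with the duplicated ALT corrected, that covers every analyte used by the permanent-stop rule.

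The choice of rule and limits belongs to the sponsor, the investigators and the HAC; none is proposed here. The cost is a wording amendment to two sections, IRB review of that amendment, and a check that the HAC charter agrees. No new visits or procedures are needed.
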